#### **5.7.4. Prohibited Medications**

The following medications are prohibited during the treatment and maintenance portions of the study:

- Any concurrent MF therapy other than that specified in the Protocol.
- Any investigational medication within 28 days or 5 half-lives, whichever is longer, before the first dose of study drug and at any time before complete withdrawal from the study.
- Use of potent inhibitors of CYP3A4 (eg, ketoconazole, clarithromycin, itraconazole, nefazodone or telithromycin, voriconazole or posaconazole; see [Appendix B](#)). Ketoconazole may be used with caution if other options are not available. Based on the low overall bioavailability of topical ketoconazole, there are no restrictions on topical ketoconazole in the study.
- Any live vaccine beginning 30 days before the first dose of study medication through the safety follow-up visit.

## **6. STUDY ASSESSMENTS**

All study assessments will be performed as indicated in the schedule of assessments ([Table 8](#)), and all laboratory assessments will be performed as indicated in [Table 9](#). [Table 10](#) presents a summary of clinical laboratory analytes to be assessed. [Table 11](#) provides the PK analysis sample collection plan. The order of assessments is suggested by the order of mention within the schedule. See Section [7](#) for instructions on each assessment. Further details of study procedures and assessments can be found in the study reference manual.

**Table 8: Schedule of Assessments – Part 1, Part 2, Part 3, and Part 4**

Visit Day (Range)	Screening Day -35 to Day -8	Baseline Day -7 to Day -1	Day 1	End of Week 2	End of Weeks 4, 8 ± 5 Days	End of Week 12 ± 5 Days	End of Weeks 16, 20 ± 5 Days	End of Week 24 ± 5 Days	Extension Visits (Q12W After Week 24) ± 7 Days	EOT or Early Termination Visit ± 5 Days	Follow-Up 30-35 Days After Last Dose of INCB050465	Survival Follow-Up Every 12 Weeks
Informed consent	X											
Contact IXRS	X		X		X	X	X	X	X	X		
Inclusion/exclusion criteria	X	X										
Prior medical & medication history	X	X										
Concomitant medication review		X	X		X	X	X	X	X	X	X	
Transfusion history/status	X	X	X		X	X	X	X	X	X	X	
Screening Symptom Form	X											
Record AEs	X	X	X	X	X	X	X	X	X	X	X	
Comprehensive physical examination	X							X				X
Targeted physical examination					X	X	X		X	X		
Spleen palpation	X	X			X	X	X	X	X	X	X	
Vital signs	X	X			X	X	X	X	X	X	X	
12-lead ECG	X							X			X	
Bone marrow biopsy a	X	X						X	X a			
MRI/CT of the upper and lower abdomen and pelvis			X			X		X	X			
Dispense and/or bring MFSAF v3.0 diary to visit		X	X		X	X	X	X				
ECOG status	X							X			X	
PGIC b					X	X	X	X	X	X		
IWG-MRT assessment c								X	X			
Modified MFSAF v3.0 diary (Appendix E)												
MPN-SAF (Appendix F)		X			X	X	X	X	X	X		
Laboratory assessments d	X	X	X	X	X	X	X	X	X	X	X	
Dispense reminder card		X	X		X	X	X	X				
Administer study drug during visit			X	X	X	X	X	X				
Dispense study drug			X		X	X	X	X		X		
Drug accountability assessment					X	X	X	X	X	X		
Survival follow-up data collection e												X

ECG = electrocardiogram; PGIC = Patient Global Impression of Change.

a Bone marrow biopsy must be completed at screening or baseline visit, unless biopsy and data from previous 2 months are available. Additional biopsies will be performed at Week 24, Week 48, and every 24 weeks.

b Patient Global Impression of Change (Appendix H).

c International Working Group response will be assessed at Week 24 and every 24 weeks thereafter.

d See [Table 9](#) and [Table 10](#).

e After discontinuation of INCB050465, the subject will remain in the follow-up phase of the study, and site staff will conduct phone calls at approximately 12-week intervals to collect data on subsequent MF therapy and survival.

**Table 9: Schedule of Laboratory Assessments – Part 1, Part 2, Part 3, and Part 4**

	Screening	Baseline	Day 1	Weeks 1, 3 (Day 8, 22) Part 1 ONLY	End of Weeks 2, 6, 10, 14, 18, 22, then Q4W	End of Weeks 4, 8, 12, 16, 20, 24, then Q12W	EOT or Early Termination Visit	Follow-Up 30-37 Days After Last Dose of INCB050465	Notes		
Window				The window for laboratory visits is ± 3 days							
Local Laboratory Assessments											
Serum chemistries	X	X*	X*	X		X	X	X	*Should be taken as close as possible to Day 1 but may be drawn up to 3 days before first dose. Only 1 sample for baseline/Day 1 is required.		
Hematology	X	X*	X*	X	X	X	X	X	*Should be taken as close as possible to Day 1 but may be drawn up to 3 days before first dose. Only 1 sample for baseline/Day 1 is required.		
Coagulation panel	X					X*	X	X	*Required Weeks 12 and 24 and Q12W.		
Urine pregnancy test		X				X*	X*		All female subjects of childbearing potential. *Pregnancy tests should be repeated if required by local regulations.		
Bone marrow biopsy, aspirate, and analysis	X*					X**			*Predose biopsy/aspirate is not required if biopsy has occurred in previous 2 months as long as biopsy/aspirate and data are available for review by investigator and/or sponsor. **Week 24 and Q24W. Samples of biopsy and unstained slides will be sent to a central vendor.		
Central Laboratory Samples*									*The central laboratory is the sponsor or sponsor's designee.		
Lipid panel (requires overnight fast)	X					X*	X		*Required Weeks 12 and 24 and Q12W.		
Serology - hepatitis and HIV	X								HBV, HCV, HIV		
Serology - CMV	X					X*			* CMV measured at Weeks 4, 8, 12, then Q12 weeks.		
Urinalysis	X					X*		X	*Required Weeks 12 and 24 and Q12W.		
Serum pregnancy	X							X	All female subjects of childbearing potential.		
FSH	X								To document hormonal menopause.		
PK samples			X		X*	X*			*PK sampling will occur on Day 1, Week 2, and Week 4 only. See Table 8 .		

**Table 9: Schedule of Laboratory Assessments – Part 1, Part 2, Part 3, and Part 4 (Continued)**

	Screening	Baseline	Day 1	Weeks 1, 3 (Day 8, 22) Part 1 ONLY	End of Weeks 2, 6, 10, 14, 18, 22, then Q4W	End of Weeks 4, 8, 12, 16, 20, 24, then Q12W	EOT or Early Termination Visit	Follow-Up 30-37 Days After Last Dose of INCB050465	Notes
Window				The window for laboratory visits is $\pm$ 3 days					

FSH = follicle-stimulating hormone; ; Q4W = every 4 weeks; Q12W = every 12 weeks; Q24W = every 24 weeks.

**Table 10: Laboratory Tests: Required Analytes**

Serum Chemistries	Hematology	Urinalysis With Microscopic Examination	Serology	Coagulation
Albumin	Complete blood count, including: Hemoglobin	Color and appearance pH and specific gravity	Hepatitis B surface antigen	PT
Alkaline phosphatase		Bilirubin	Hepatitis B surface antigen antibody	PTT
ALT	Hematocrit	Glucose	Hepatitis B core antibody	INR
AST	Platelet count	Ketones	HBV-DNA	
Bicarbonate	Red blood cell count	Leukocytes	HCV antibody	
Blood urea nitrogen	White blood cell count	Nitrite	HCV-RNA	
Calcium	Blasts	Occult blood	CMV DNA	
Chloride		Protein	HIV testing	
Creatinine		Urobilinogen		
Glucose	Differential count, including: Basophils			
Lactate dehydrogenase	Eosinophils			
Phosphate	Lymphocytes			
Potassium	Monocytes			
Sodium	Neutrophils			
Total bilirubin	Blasts			
Direct bilirubin (if total bilirubin is elevated above ULN)	Absolute values must be provided for: Lymphocytes			
Total protein	Neutrophils			
Uric acid				
		Lipid Panel	Other	Pregnancy Testing
		Total cholesterol Triglycerides LDL HDL	FSH (only at screening to verify hormonal menopause)	Female subjects of childbearing potential only require a serum test at screening and a urine pregnancy test before the first dose on Day 1. Pregnancy tests (serum or urine) should be repeated if required by local regulations.

HDL = high-density lipoprotein; INR = international normalized ratio; LDL = low-density lipoprotein; PTT = partial thromboplastin time; PT = prothrombin time.

Note: Additional tests may be required, as agreed by investigator and sponsor, based on emerging safety data.

**Table 11: Schedule of Pharmacokinetic Sampling for Part 1, Part 2, Part 3, and Part 4**

Study Day 1	Week 2	Week 4

Subject arrives having withheld both INCB050465 and ruxolitiniba
 
Predose sample = Time 0 sample
 
Administer ruxolitinib
 
Timed samplesb:
 
 
1 hour postdose
 
2 hour postdosec
 
4 hour postdose
 
 
Administer INCB050465
	
Subject arrives having withheld both INCB050465 and ruxolitiniba
 
Predose sample = Time 0 sample
 
Administer INCB050465
 
Timed samplesb:
 
 
1 hour postdose
 
2 hour postdosec
 
4 hour postdose
 
 
Administer ruxolitinib
	
Subject arrives having withheld both INCB050465 and ruxolitiniba
 
Predose sample = Time 0 sample
 
Administer INCB050465 plus ruxolitinib
 
Timed samplesb:
 
 
1 hour postdose
 
2 hour postdosec
 
4 hour postdose
 

a Subjects are also to arrive at the study visits in the fasted state.

b Window for 1-, 2-, and 4-hour collections is  $\pm$  15 minutes.

c Subjects may eat after the 2-hour timepoint sample has been drawn.

## 6.1. Screening

Screening is the interval between signing the ICF and the beginning of the 7-day baseline period (ie, Day -35 to Day -8). Screening may not exceed 28 days. Assessments that are required to demonstrate eligibility may be performed over the course of 1 or more days during the screening process.

Subjects should arrive for the screening visit after an overnight fast of at least 8 hours or since midnight. A subject who has not fasted should be scheduled for the screening assessment blood draws on a morning when he/she can arrive after an overnight fast of at least 8 hours or since midnight.

Procedures conducted as part of the subject's routine clinical management (eg, blood count, serum chemistry) and obtained before signing of informed consent may be used for screening provided that the procedure meets the Protocol-defined criteria and has been performed in the timeframe of the study (ie, up to 28 days before Day 1). All information associated with eligibility requirements must be entered into the appropriate CRF pages. Eastern Cooperative Oncology Group assessment will be used to stratify subjects for Parts 2, 3, and 4 and must be reported via IXRS at the time.

Bone marrow biopsy (and additional aspirate collection) for confirmation of MF diagnosis and degree of fibrosis must be performed at the screening or baseline visit intervals. NOTE: Subjects without circulating blasts at the screening hematology assessment may use a historical biopsy obtained within 2 months before screening, and all data and reports are available for investigator's review. Subjects without a prior biopsy report as indicated above must have a biopsy at screening or baseline or will not be able to enroll in the study. The prior data will need to be entered into the CRF for this study, with explanation as to the origin of the data (date of biopsy/aspirate).

Results from the screening visit evaluations will be reviewed to confirm subject eligibility before enrollment/randomization or the administration of study drug. Tests with results that fail eligibility requirements may be repeated once during screening if the investigator believes the results to be in error. For screening assessments that are repeated, the most recent available

result before randomization/treatment assignment will be used to determine subject eligibility. Treatment should start as soon as possible, but within 3 days after the date of enrollment/randomization. Additionally, a subject who fails screening may repeat the screening process 1 time if the investigator believes that there has been a change in eligibility status (eg, after recovery from an infection). In this case, a new subject number must be assigned via IXRS.

## 6.2. Baseline

Subjects who have signed the ICF and meet all the entry criteria (see Section 3) may be enrolled in the study and will be contacted by clinical site staff to schedule the baseline visit. The baseline interval corresponds to the 7 days before initiating treatment with INCB050465 and during which the baseline MRI (or CT scan in applicable subjects) and symptom diary will be initiated.

- The modified MFSAF v3.0 diary ([Appendix E](#)) should be distributed. Subjects will be issued a hand-held device and will complete the diary questions each night beginning on Day -7 up to the Week 24 visit. Subjects will be instructed to place the device on the docking station (also provided) for automatic data transmittal each night after completing the questions. Subjects will be instructed to leave the device in the docking station when not answering the questions so that the unit remains fully charged. Subjects will receive training on the device by study site staff before leaving the site. Subjects will bring the device with them to study visits on Day 1, Week 4, Week 8, Week 12, Week 16, and Week 20 so that the device charging can be verified and to download accumulated data. The device will then be returned to the subject at these same visits for continued use each night. Subjects will return the device and the docking station for the final time at the Week 24 Visit, so that all data can be archived.
- The MRI (or CT scan in applicable subjects) should be conducted on the first or second day of the baseline interval to allow ample time for the laboratory to verify scan quality.
- Blood samples for hematology and serum chemistry analyses should be taken as close as possible to Day 1 but may be drawn up to 3 days before first dose of INCB050465. This blood sample will serve as the pre-INCB050465 baseline sample; a Day 1 sample is not required provided the baseline sample is within 3 days of the first dose of INCB050465.

## 6.3. Treatment

The treatment period begins with the first dose of INCB050465 (Day 1) through the point at which the investigator determines the subject will be permanently discontinued from study drug.

There will be study visits and laboratory-only visits in the study. [Table 8](#), [Table 9](#), and [Table 10](#) provide the scheduled assessments for each study visit and laboratory-only visit.

Subjects will have a regularly scheduled study visit at screening, baseline, Day 1, and after 4, 8, 12, 16, 20, and 24 weeks of treatment (ie, visits designated Week 4, Week 8, Week 12, Week 16, Week 20, and Week 24) and then every 12 weeks thereafter if continuing on treatment, where blood samples, spleen measurements, and other assessments will be obtained. There is also a

study visit at the end of 2 weeks treatment (designated visit Week 2) for PK sampling, AE assessment and hematology blood draws. The visit window is  $\pm$  5 days for visits through Week 24 and  $\pm$  7 days for visits in the extension portion. The timing for study visits will be based on the date of the Day 1 visit when treatment with INCB050465 is initiated.

All serology, lipid profile, and urinalysis laboratory assessments collected at the visits in [Table 9](#) will be analyzed by a central laboratory. Serum chemistry, hematology, and coagulation parameters will be assessed using local laboratories. Where needed, urine pregnancy will be assessed by local lab. Bone marrow biopsy samples will be assessed for MF characteristics by local lab; subsequent studies using remaining material will be conducted by sponsor or its designee. [REDACTED] PK samples will be collected and analyzed by the sponsor or sponsor's designee. Subjects will arrive for all study visits (including Week 2, not at laboratory-only visits) having withheld the morning dose of ruxolitinib and INCB050465 and in the fasted state; administration will occur in the clinic (first 24 weeks only). Subjects should be told to bring a snack or small meal to the study visits, as they will arrive for the visits in the fasted state.

Subjects will have laboratory-only visits to collect hematology lab samples as noted in [Table 10](#). Subjects participating in Part 1 will have additional laboratory assessments performed at Week 1 (ie, Day 8) and Week 3 (ie, Day 22). The window for laboratory visits is  $\pm$  3 days. Subjects in Parts 2, 3, and 4 may visit a local laboratory for the interim hematology assessments provided that the laboratory data and corresponding normal ranges can be scanned and emailed to the investigative site; interim laboratory visits at the study site laboratory are preferred. Additional laboratory assessments may be performed at the investigator's discretion, including following changes in dose, or if laboratory parameters are at Grade 3 or Grade 4 levels based on the CTCAE v4.03.

Subjects will have an MRI of the upper and lower abdomen and pelvis to determine the spleen volume at baseline, at Week 12 and Week 24, and every 12 weeks thereafter through Week 108. Computed tomography scan will be substituted for subjects who are not candidates for MRI or when MRI is not readily available. Patients Global Impression of Change questionnaire ([Appendix H](#)) will be completed at each study visit. Determination of spleen length below the left costal margin will be measured by palpation at each study visit.

Subjects will complete an electronic symptom diary (MFSAF v3.0) daily from baseline through the Week 24 visit (total of 25 weeks; [Appendix E](#)).

Subjects will complete the MPN-SAF ([Appendix F](#)) at visits noted in [Table 8](#).

#### **6.4. End of Treatment**

There is no predefined EOT. When the subject permanently discontinues INCB050465, the EOT visit should be conducted. If the EOT visit coincides with a regular study visit, then the EOT evaluations will supersede those of that scheduled visit, and the data should be entered in the EOT visit in the CRF. The subject should be encouraged to return for the follow-up visit.

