### 5.6.2. Withdrawal Procedures

**The decision to discontinue study treatment (eg, INCB050465 and ruxolitinib) will not constitute study withdrawal or study completion.** In the event that the decision is made to discontinue study treatment, the treatment portion will be considered complete and the follow-up portion will begin. Subjects who discontinue treatment with the study drug will be followed for subsequent MF treatment regimens and survival.

Upon discontinuation of study treatment, the EOT visit should be completed as outlined in the schedules of assessments ([Table 8](#) and [Table 9](#)). The date of the last dose of study drug will be recorded in the CRF, and the reason for subject withdrawal will be recorded. After discontinuation of study treatment, the subject will remain in the follow-up portion of the study, and site staff will conduct phone calls at approximately 12-week intervals to the study subject to collect data on subsequent MF treatment regimens and survival.

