### **7.6.3. Imaging**

The primary measure of spleen size will be by MRI (or CT scan in applicable subjects). An MRI of the upper and lower abdomen and pelvis will be performed at baseline, Week 12 and Week 24, and every 12 weeks thereafter through Week 108. An MRI will be performed with a body coil because the objective is to measure organ volume, not to find very small lesions. The MRIs will be read initially by local radiologists who will assess the scan for quality and send all scans (MRI or CT) to the central imaging laboratory the same day, if at all possible. The scans from an individual subject will be read by a central reader. Spleen and liver volume will be obtained by outlining the circumference of the organ and determining the volume using the validated technique of least squares. The MRI will not determine spleen length below the costal margin, as there are no validated approaches for determining this measurement. Procedure-specific training for scanning and image capture will be provided by the vendor.

An MRI is the preferred method for obtaining spleen volume data. However, CT scans may be performed at the visits where MRI is designated if the subject is not a candidate for MRI (eg, because of the presence of metal clips in the body, because of claustrophobia) or if MRI is not readily available. CT scans will be similarly processed by the same central laboratory as used for MRIs. Procedure-specific training for scanning and image capture will be provided by the vendor. NOTE: The same method (MRI vs CT) must be used for all visits for a given subject unless a new contraindication to the use of MRI occurs (eg, pacemaker insertion).

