#### **9.4.1. Efficacy Analyses**

##### **9.4.1.1. Primary Efficacy Analyses**

The primary endpoint is change in percentage spleen volume from baseline at 12 weeks as measured by MRI (or CT scan in applicable subjects). Statistical comparisons between treatment groups for the primary endpoint will only be performed between subjects randomized to TG5D and TG5I/M + TG5 in Parts 3 and 4 of the study.

A location shift in percentage change in spleen volume between TG5D and TG5I/M accounting for stratification by ECOG performance status at screening (ECOG 0-1 vs 2) will be assessed using a van Elteren test ([van Elteren 1960](#)).

Within each stratum, subjects who discontinue from the study or who have missing values for the Week 12 spleen volume will be imputed as having the largest possible increase in percentage spleen volume and given the lowest rank in the stratum. The subject with the largest percentage reduction in spleen volume in a stratum will be given the highest rank within the stratum. In the case of ties, average ranks will be assigned.

If the randomized portion of the study fails to enroll a sufficient number of subjects in a particular stratum, then the primary endpoint will be assessed using a 2-sample Wilcoxon rank sum test with a normal approximation applied to the test statistic, for purposes of calculation stability. Ranking will be carried out using the same approach but without stratification.

Results for subjects enrolled to TG10 and TG20 will be summarized descriptively with no formal statistical comparisons performed.

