7.3. Analysis of the Primary Efficacy Parameter

7.3.1. Primary Efficacy Analysis

The primary endpoint is change and percentage change in spleen volume from baseline at 12 weeks as measured by MRI (or CT scan in applicable participants). A location shift in percentage change in spleen volume between TG5D and TG5I/M for stratification by ECOG performance status at screening (0 or 1 vs 2) will be assessed using a van Elteren test ([van Elteren 1960](#)).

The baseline spleen volume will be measured by MRI (or by CT for applicable participants) during the baseline visit (Days -7 to 1); the last value will be used if there are multiple values measured during the baseline visit.

The Week 12 spleen volume will be measured by MRI (or by CT for applicable participants) during the Week 12 visit (Day 84 ± 7 days); the last value will be used if there are multiple values measured during the Week 12 visit.

Within each stratum, participants who discontinue from the study or who have missing values for the Week 12 spleen volume will be imputed as having the largest possible percentage increase in spleen volume and given the lowest rank in the stratum. The participant with the largest percentage reduction in spleen volume in a stratum will be given the highest rank within the stratum. In the case of ties, average ranks will be assigned.

If the study fails to enroll a sufficient number of participants in a particular stratum, a sensitivity analysis using a 2-sample Wilcoxon rank sum test with a normal approximation applied to the test statistic, for purposes of calculation stability, will be conducted. Ranking will be carried out using the same approach but without stratification.

Results for participants enrolled to TG10 or TG20 will be summarized descriptively with no formal statistical comparisons performed.

Statistical comparison will be conducted for TG5D versus TG5 (TG5I/M). To explore the difference in daily dosing and daily/weekly dosing, the statistical comparison will also be performed for daily dosing (TG5D + TG5I/M) versus daily/weekly dosing (TG10 + TG20).

In the event of a single-arm trial, a 95% CI for median percentage change in spleen volume from baseline at Week 12 will be calculated from the exact binomial distribution.

The percentage change from baseline at Week 12 will be calculated using the formula:

$$\% \text{ change} = 100 \times [\text{Week 12 spleen volume} - \text{baseline spleen volume}] / \text{baseline spleen volume}$$

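### Protocol 6.4 conflicts with 6.3 and 7.6.3: when end of treatment falls on the Week 12 or Week 24 visit, the scheduled spleen scan can be skipped and the subject ranked worst because it is missing

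*Protocol*

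**What the plan says.** **Visit rule.** Protocol 6.4 covers an EOT visit that falls on a regular visit: "If the EOT visit coincides with a regular study visit, then the EOT evaluations will supersede those of that scheduled visit". The data then go under EOT in the CRF.

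**What EOT contains.** Protocol 5.6.2: "Upon discontinuation of study treatment, the EOT visit should be completed as outlined in the schedules of assessments", meaning Tables 8 and 9. The Table 8 row "MRI/CT of the upper and lower abdomen and pelvis" has four marks and none at EOT. The bone marrow biopsy and IWG-MRT rows also have no EOT mark.

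**Imaging schedule.** Protocol 7.6.3 says the MRI "will be performed at baseline, Week 12 and Week 24, and every 12 weeks thereafter through Week 108". Protocol 6.3 gives the same times. Neither names EOT as a scan time, and neither makes an exception when EOT falls in a scan week.

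**Missing scans.** Protocol 9.4.1.1 covers subjects "who have missing values for the Week 12 spleen volume will be imputed as having the largest possible increase in percentage spleen volume". SAP 7.3.1 matches it: "participants who discontinue from the study or who have missing values for the Week 12 spleen volume will be imputed", with the result that they "will be imputed as having the largest possible percentage increase in spleen volume and given the lowest rank in the stratum". SAP 7.4.1 applies the same analysis to Week 24.

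**Scan window.** SAP 7.3.1 takes the volume measured "during the Week 12 visit (Day 84 ± 7 days"). It does not say what to do with a scan filed under EOT.

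**The concern.** Two Protocol instructions meet at the same visit and give different answers, and nothing says which prevails. Section 6.4 is the only one that addresses coinciding visits, so a site could reasonably follow it and do only the EOT assessments.

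No later step recovers the scan. After EOT, the schedule has a safety visit and contacts about every 12 weeks on survival and subsequent MF treatment, with no imaging.

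The subject is still analysed. Protocol 5.6.2 says that stopping study treatment is not study withdrawal, and SAP 5.3.2 keeps subjects who stopped treatment on or before the week in question in the spleen volume evaluable population. A visit-labelling rule could therefore turn a measurable outcome into the worst rank in the primary test. The trial is open-label (Protocol 4.2), so such losses need not be equal between groups. The futility count uses the same Week 12 scan. At Week 24 the secondary spleen volume is exposed in the same way, as are the biopsy and IWG-MRT assessment due then.

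**Working it through.** **Inputs (Protocol 9.2).** n = 30 per group, shift 11.4 percentage points, common SD 14.5, two-sided α = 0.10, Wilcoxon rank sum with normal approximation, planned power 90%.

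**Step 1: reproduce the planned power.**
- Two-sample normal formula: 11.4 / (14.5 × √(2/30)) = 3.045; Φ(3.045 − 1.645) = 91.9%.
- With the Wilcoxon efficiency factor 3/π, effective n = 30 × 3/π = 28.65 and power is 90.8%.
- Simulation of the rank test itself (40,000 runs): 90.1%.

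The stated 90% is confirmed.

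**Step 2: set k scans to the worst value.** In the simulation, k subjects in a group were tied at the largest increase whatever their true change, and average ranks were used. With N = 60 and W the rank sum of one group,

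Z = (W − 30 × 61/2) / s, where s² = [30 × 30 / (60 × 59)] × (Σr² − 60 × 61²/4),

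and the test rejects if |Z| > 1.645. The documents give no rate of stopping at Week 12, so every k is an assumption.

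| Scans lost (k) | Power, k in each group | Power, better group only | Power, worse group only | Rejection with no true difference, one group only |
|---|---|---|---|---|
| 0 | 90.1% | 90.1% | 90.1% | 9.8% |
| 1 | 87.3% | 83.5% | 92.6% | 10.0% |
| 2 | 84.1% | 74.0% | not run | 11.6% |
| 3 | 79.8% | 61.3% | 96.3% | 15.4% |

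**Step 3: futility count.** Under the Protocol 9.5.2 rule (stop a group if fewer than 4 of 15 have change ≤ 0%), P(stop) = P(X ≤ 3) with X ~ Bin(15, p). This reproduces Protocol Table 16: 99.5, 94.4, 64.8, 46.1, 29.7, 9.1 and 1.8%. If m of the 15 scans are missing and count as failures (an assumption), X ~ Bin(15 − m, p). At p = 40%, stopping rises from 9.1% to 12.4%, 16.9% and 22.5% for m = 1, 2 and 3.

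**Step 4: who is exposed.** Only a subject whose EOT coincides with Week 12 and who has no scan from Day 84 − 7 = 77 to Day 84 + 7 = 91.

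**The case against.** The strongest reply is that nothing is necessarily lost. Sections 6.3 and 7.6.3 require the Week 12 scan with no exception, and 6.4 can be read as a rule on visit precedence and data entry, not as a cancellation of imaging. This stands in part: the scan can be lost, but it is not shown that it will be.

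A reader might infer that a scan filed under EOT is discarded. The documents do not support that. SAP 7.3.1 defines the visit by study day and does not restrict it by CRF label, so a scan on Day 84 entered under EOT fits the window. What is missing is a sentence saying so.

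A reader might also infer that stops will cluster at Week 12, or differ between the two regimens. No stopping rate is given for either group, and the withdrawal criteria in Protocol 5.6.1 list no spleen-volume or lack-of-response criterion. A stop prompted by the Week 12 scan also implies that the scan exists.

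The one-sided scenarios look severe, but they are the extremes. One loss in one group with no true difference gives 10.0% rejection, so no inflation. Losses in the worse group raise power, which is equally an artefact. If those who stop are genuinely poor responders, the lowest rank costs less than shown.

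Column alignment in the extracted text of Table 8 is not secure: the baseline MRI mark sits under Day 1, and the EOT ECG required by 7.5.4 sits under Follow-Up. The absence of EOT imaging does not depend on alignment, however. The row's four marks match the four times named in the text, leaving none for EOT.

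Finally, SAP 5.2 and 10.2.3 record early termination, so figures for 30 per group describe the planned design, and a rule that stops enrollment matters less now.

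**Conclusion.** The conflict is real. Followed literally, 6.4 can remove the Week 12 primary scan or the Week 24 secondary scan, and the lowest rank then results from the missing scan alone. Only the Week 12 loss touches the primary endpoint.

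The size is unknown. The power and rejection figures in the working show sensitivity under assumed losses of 1 to 3 scans; they are not a forecast. They rest on 30 per group, normal data with SD 14.5, a single stratum, fixed counts of missing scans, and losses unrelated to true response. The documents support neither a certain loss nor a demonstrated bias between groups. This is a low-cost improvement and not a must-fix.

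**What to change.** **Protocol 6.4.** State that when EOT falls within the window of a scheduled visit, the MRI/CT already due at that visit is still obtained, and likewise the other efficacy assessments already due at Week 24 (biopsy and IWG-MRT assessment).

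**SAP 7.3.1 and 7.4.1.** State that spleen scans are assigned to Week 12 or Week 24 by scan date (Day 84 ± 7 or Day 168 ± 7), whatever the CRF visit label, including EOT. Section 7.4.1 prints no day window of its own; Day 168 ± 7 carries over the Week 12 width and matches the Week 24 window in SAP 7.4.2.1.

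**Cost.** One sentence in the Protocol, one rule in the SAP and minor programming. No procedure is added beyond what is already scheduled for that week. Because enrollment has ended, the Protocol change may recover little; the SAP sentence mainly protects scans already filed under EOT.
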